12.4 Schedule of Procedures/Evaluations: Timing and Definitions

12.4.1 Screening: The period that commences at the signing of informed consent and ends when subjects are either (1) informed that they are not eligible for participation; (2) informed that they are eligible but decline participation; or (3) informed that they are eligible, choose to participate, and are scheduled for a baseline assessment and randomized.

12.4.2 Enrollment: For IRB purposes, participants who sign a consent form are considered to be enrolled. However, the sample size of 60 refers to the number of individuals who screen, are eligible, choose to participate, and are randomized to treatment.

12.4.3 HIV Counseling and Testing: Individuals will not be invited to screen for the study unless they are known to have HIV infection. Thus HIV counseling and testing will not take place under this protocol.

12.4.4 Follow-Up: Please see description of follow-up visits in section 12.1

12.4.5 Early Termination Visit: Subjects who end the study early will be asked come for a study termination visit (please see Appendix A).

12.4.6 Pregnancy Visit: Every effort will be made, both through absolute eligibility criteria and ongoing counseling about contraception and risk for participating women of child-bearing age, to prevent pregnancy during the study. Should pregnancy occur, a participant would be asked to discontinue the medication immediately and to come for a visit in order to discuss the situation with the Site PI. Such participants would also be asked to remain in contact with the PI and study team through the completion of the pregnancy in order to document the outcome.

12.4.7 Other Visits: Aside from the visits described in this section and in 12.1, no other visits are anticipated.

12.4.8 Final Study Visit: Please see description of 18 month visit above. Subjects who leave the study early will be asked to come for an early termination visit in lieu of their next scheduled study visit as discussed above.

13. ASSESSMENT OF SAFETY

13.1 Safety Assessment Overview

Assessment of safety will be performed by a study investigator at each visit, with subjects asked to describe any changes or adverse effects that they have noted since the previous study visit. In addition, subjects will be repeatedly asked to call the study team if they experience any adverse effects, have any new medical conditions, start any new medications, have any procedures, or require hospitalization, such that safety can be monitored between study visits. All adverse events will be collected and reported as described below. The Co-PI's ([name] and [name]) will periodically review adverse events, and the study will also be monitored by the NIAID and the FDA, as the protocol is conducted under an IND for tesamorelin (77,473 to [name]).

13.2 Adverse Event Procedures and Reporting Requirements

At each contact with the subject, information regarding adverse events will be elicited by appropriate questioning and examinations and will be:

- immediately documented in the subject's medical record/source document,
- recorded on the Adverse Event Case Report Form (AE CRF) or electronic database, and
- reported as outlined below (e.g., IND Sponsor, IRB).

13.2.1 Definitions

Adverse Event (AE)

An adverse event is any untoward or unfavorable medical occurrence in a human subject, including any abnormal sign (e.g., abnormal physical exam or laboratory finding), symptom, or disease, temporally associated with the subject's participation in the research, whether or not considered related to the research.

Adverse Reaction (AR)

An adverse event that is caused by an investigational agent (drug or biologic).

Suspected Adverse Reaction (SAR)

An adverse event for which there is a reasonable possibility that the investigational agent caused the adverse event. 'Reasonable possibility' means that there is evidence to suggest a causal relationship between the drug and the adverse event. A suspected adverse reaction implies a lesser degree of certainty about causality than adverse reaction which implies a high degree of certainty.

Serious Adverse Event (SAE)

A Serious Adverse Event is an AE that results in one or more of the following outcomes:

- death
- a life threatening (i.e., an immediate threat to life) event
- an inpatient hospitalization or prolongation of an existing hospitalization
- a persistent or significant incapacity or substantial disruption of the ability to conduct normal life functions
- a congenital anomaly/birth defect
- a medically important event*

* Medical and scientific judgment will be exercised in deciding whether expedited reporting is appropriate in other situations, such as important medical events that may not be immediately life

threatening or result in death or hospitalization but that may jeopardize the subject or may require intervention to prevent one of the other outcomes listed above.

Unexpected Adverse Event

An AE is unexpected if it is not listed in the Investigator's Brochure or Package Insert (for marketed products) or is not listed at the specificity or severity that has been observed. It is the responsibility of the IND Sponsor to make this determination.

Serious and Unexpected Suspected Adverse Reaction (SUSAR)

A SUSAR is a Suspected Adverse Reaction that is both Serious and Unexpected.

Unanticipated Problem (UP)

An Unanticipated Problem is any event, incident, experience, or outcome that is

1. unexpected in terms of nature, severity, or frequency in relation to
 - a. the research risks that are described in the IRB-approved research protocol and informed consent document; Investigator's Brochure or other study documents; and
 - b. the characteristics of the subject population being studied; and
2. possibly, probably, or definitely related to participation in the research; and
3. places subjects or others at a greater risk of harm (including physical, psychological, economic, or social harm) than was previously known or recognized. (Per the IND Sponsor, an AE with a serious outcome will be considered increased risk.)

Unanticipated Problem that is not an Adverse Event (UPnonAE)

Unanticipated problem that is not an Adverse Event (UPnonAE): An unanticipated problem that does not fit the definition of an adverse event, but which may, in the opinion of the investigator, involve risk to the subject, affect others in the research study, or significantly impact the integrity of research data. Such events would be considered a non-serious UP. For example, we will report occurrences of breaches of confidentiality, accidental destruction of study records, or unaccounted-for study drug.

Protocol Deviation: Any change, divergence, or departure from the IRB approved study procedures in a research protocol. Protocol deviations are designated as serious or non-serious and further characterized as

1. Those that occur because a member of the research team deviates from the protocol.
2. Those that are identified before they occur, but cannot be prevented.
3. Those that are discovered after they occur

Serious Protocol Deviation: A deviation that meets the definition of a Serious Adverse Event or compromises the safety, welfare or rights of subjects or others.

Non-compliance: The failure to comply with applicable NIH HRPP policies, IRB requirements, or regulatory requirements for the protection of human subjects. Non-compliance is further characterized as

1. Serious: Non-compliance that
 - a. Increases risks, or causes harm, to participants
 - b. Decreases potential benefits to participants
 - c. Compromises the integrity of the NIH-HRPP
 - d. Invalidates the study data
2. Continuing: Non-compliance that is recurring
3. Minor: Non-compliance that, is neither serious nor continuing.

13.2.2 Investigator Reporting Responsibilities to the IND Sponsor

Adverse Events

Line listings, frequency tables, and other summary AE data will be submitted to the IND Sponsor when needed for periodic safety assessments, review of IND annual reports, review of IND safety reports, and preparation of final study reports.

Serious Adverse Events

All SAEs (regardless of relationship and whether or not they are also UPs) must be reported to the IND Sponsor within 1 business day of site awareness. Any SAE submitted to the FDA will also be submitted to the DAIDS Clinical Representative within 24 hours of FDA notification. SAEs that are unexpected and deemed to be possibly related to the study drug will also be reported to both IRBs, regardless of the site at which they occur.

Unanticipated Problems

Unanticipated Problems that are also adverse events must be reported to the IND Sponsor and the DAIDS Clinical Representative no later than 7 calendar days of site awareness of the event. UPs that are not AEs are not reported to the IND Sponsor.

Pregnancy

Pregnancy itself is not an AE. However, complications of pregnancies are AEs and may be SAEs. Pertinent obstetrical information for all pregnancies will be reported to the IND Sponsor via fax or email within 3 business days from site awareness of the pregnancy.

Pregnancy outcome data (e.g., delivery outcome, spontaneous or elective termination of the pregnancy) will be reported to the IND Sponsor within 3 business days of the site's awareness.

In the event of a pregnancy, the DSMB and the IRB will be notified. The participant will

- Discontinue the study agent
- Withdraw from the study but continue in follow-up for safety
- Be advised to notify her obstetrician of study agent exposure

13.2.3 Reporting Procedures to the NIAID IRB

Expedited Reporting to the NIAID IRB

Serious and non-serious Unanticipated Problems, deaths, serious deviations, and serious or continuing non-compliance will be reported within 7 calendar days of investigator awareness. Serious Adverse Events that are possibly, probably, or definitely related to the research will be reported to the NIAID IRB within 7 calendar days of investigator's awareness, regardless of expectedness.

Annual Reporting to the NIAID IRB

The following items will be reported to the NIAID IRB in summary at the time of Continuing Review:

- Serious and non-serious unanticipated problems
- Expected serious adverse events that are possibly, probably, or definitely related to the research
- Serious adverse events that are not related to the research
- All adverse events, except expected AEs and deaths granted a waiver of reporting.
- Serious and Non-Serious Protocol deviations

- Serious, continuing, and minor non-compliance
- Any trends or events which in the opinion of the investigator should be reported

13.2.4 Reporting Procedures to the MGH IRB

Partners Human Research Committee policy dictates the following reporting procedures.

Expedited Reporting to the MGH IRB

The following will be reported within 7 calendar days of investigator awareness:

- Internal adverse events that are unexpected, and related or possibly related to the research and that indicate there are new or increased risks to subjects
- External adverse events that are serious, unexpected, and related or possibly related to the research and that indicate there are new or increased risks to subjects that require some action (e.g., modification of the protocol, consent process, or informing subjects)
- Deviation from the approved research protocol or plan without IRB approval in order to eliminate apparent immediate hazard to subjects or harm to others
- Deviation from the approved research protocol or plan that placed subjects or others at an increased risk of harm regardless of whether there was actual harm to subjects or others
- Breach of confidentiality or violation of HIPAA (e.g., lost or stolen laptop)
- Medication, procedural or laboratory error (e.g., errors in drug administration or dosing, surgical or other procedure, or testing of samples or test results) regardless of whether subjects experienced any harm
- Interim analysis, safety monitoring report, publication in a peer-reviewed journal, or other finding that indicates that there are new or increased risks to subjects or others or that subjects are less likely to receive any direct benefits from the research
- Change in FDA labeling (e.g., black box warning), withdrawal from market, manufacturer alert from the sponsor, or recall of an FDA-approved drug, device, or biologic used in the research
- Complaint by/on behalf of a research subject that indicates that the rights, welfare, or safety of the subject have been adversely affected or that cannot be resolved by the investigator
- Incarceration of a research subject during participation in research that is not approved for involvement of prisoners as subjects
- Noncompliance with applicable regulations or requirements or determinations of the IRB identified by the research team or others (e.g., FDA Form 483 or Warning Letter) that indicates that the rights, welfare, or safety of subjects have been adversely affected
- Suspension or termination of the research, in whole or in part, based on information that indicates that the research places subjects at an increased risk of harm than previously known or recognized (e.g., FDA clinical hold)
- Suspension or disqualification of an investigator by FDA, sponsor, or others
- Scientific misconduct
- Any other problem that indicates that the research places subjects or others at an increased risk of harm or otherwise adversely affect the rights, welfare or safety of subjects or others.

Annual Reporting to the MGH IRB

The following items will be reported to the MGH IRB in summary at the time of Continuing Review:

- Serious and non-serious unanticipated problems

- Expected serious adverse events that are possibly, probably, or definitely related to the research
- Serious adverse events that are not related to the research
- All adverse events
- Serious and Non-Serious Protocol deviations
- Serious, continuing, and minor non-compliance
- Any trends or events which in the opinion of the investigator should be reported

13.2.5 Follow-up of Adverse Events and Serious Adverse Events

AEs that occur following enrollment of the subject (by signing the informed consent) are followed until the final outcome is known or until the end of the study follow-up period.

SAEs that have not resolved by the end of the follow-up period are followed until final outcome is known. If it is not possible to obtain a final outcome for an SAE (e.g., the subject is lost to follow-up), the reason a final outcome could not be obtained will be recorded by the investigator on the AE CRF (if the CRF is still open).

SAEs that occur after the study follow-up period that are reported to and are assessed by the Investigator to be possibly, probably, or definitely related must be reported to the IND Sponsor, as described above.

14. CLINICAL MANAGEMENT

Clinical Management of Adverse Events

If a diagnosis is clinically evident (or subsequently determined), the diagnosis rather than the individual signs and symptoms or lab abnormalities will be recorded as the AE.

All AEs occurring from the time the informed consent is signed through the study follow-up period will be documented, recorded, and reported.

The Investigator will evaluate all AEs with respect to **Seriousness** (criteria listed above), **Severity** (intensity or grade), and **Causality** (relationship to study agent and relationship to research) according to the following guidelines.

Severity

The Investigator will grade the severity of each AE according to the "Division of AIDS Table for Grading the Severity of Adult and Pediatric Adverse Events" Version 2.0, November, 2014, which can be found at:

<https://rsc.niaid.nih.gov/clinical-research-sites/daids-adverse-event-grading-tables>

Some grade 1 lab parameters on the DAIDS Toxicity Table (Fibrinogen, Potassium (low), Uric Acid (males only, elevated)) fall within the NIH lab reference range for normal values. These normal values will not be reported as grade 1 adverse events. The grade 1 values for these tests will be reported as follows:

- Fibrinogen: 100-176 mg/dL
- Potassium (low): 3.0-3.3 mmol/L
- Uric Acid (males): 8.7-10.0 mg/dL

Causality

Causality (likelihood that the event is related to the study agent) will be assessed considering the factors listed under the following categories:

Definitely Related

- reasonable temporal relationship
- follows a known response pattern
- clear evidence to suggest a causal relationship
- there is no alternative etiology

Probably Related

- reasonable temporal relationship
- follows a suspected response pattern (based on similar agents)
- no evidence of a more likely alternative etiology

Possibly Related

- reasonable temporal relationship
- little evidence for a more likely alternative etiology

Unlikely Related

- does not have a reasonable temporal relationship
OR
- good evidence for a more likely alternative etiology

Not Related

- does not have a temporal relationship
OR
- definitely due to an alternative etiology

Note: Other factors (e.g., dechallenge, rechallenge) should also be considered for each causality category when appropriate. Causality assessment is based on available information at the time of the assessment of the AE. The investigator may revise the causality assessment as additional information becomes available.

14.1 Other Disease Events

Occurrence of other disease events will be immediately brought to the attention of the Site PI. The participant's clinical care providers will be contacted to discuss his/her participation in the study and to discuss whether or not the study drug should be discontinued, either temporarily or permanently, and whether or not the participant can safely continue in the protocol.

14.2 Pregnancy

Women able to bear children will be repeatedly counseled about the risks of pregnancy during the study and the importance of contraception, and women will be instructed to immediately discontinue the study drug if they suspect pregnancy. If a participant becomes pregnant during the study, she will

- Discontinue the study agent
- Withdraw from the study but continue in follow-up for safety
- Be advised to notify her obstetrician of study agent exposure

14.3 Criteria for Discontinuation

14.3.1 Criteria for Permanent Intervention Discontinuation for an Individual Participant

The criteria for permanent discontinuation of further study intervention for an individual participant are

- Fasting glucose >150mg/dL, or >180 mg/dL for individuals with known type 2 diabetes at study entry, at any visit, confirmed by re-draw
- Erythema and/or pruritis extending ≥ 3 cm beyond the immediate injection site, indicating allergic reaction
- Pregnancy
- Active malignancy
- Evolving medical condition (e.g., progressive liver disease, acute critical illness) such that continued participation in the study may incur risk will also be discontinued.
- Significant symptoms of GH excess felt to be related to the study drug
- IGF-1 level that remains ≥ 3 standard deviations above the mean following a dose adjustment
- Development or worsening of retinopathy
- Clinical conditions, which in the best judgment of the investigator are believed to be harmful or potentially life-threatening to the participant, even if not felt to be related to the study drug and/or not addressed in the AE management section of the protocol.
- Request by participant to terminate study product(s)/intervention(s)

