10. STUDY POPULATION

10.1 Inclusion/Exclusion Criteria

10.1.1 60 HIV-infected subjects will be enrolled in this 18 month study. Inclusion criteria:

- Men and women 18-70yo
- HIV-infection and treatment with a stable antiretroviral regimen for ≥ 3 months. HIV-status will be documented with any one of the following:
 - Documentation of HIV diagnosis in the medical record by a licensed health care provider;
 - OR HIV-1 RNA detection by a licensed HIV-1 RNA assay demonstrating > 1000 RNA copies/mL;
 - OR any licensed HIV screening antibody and/or HIV antibody/antigen combination assay confirmed by a second licensed HIV assay such as a HIV-1 Western blot confirmation or HIV rapid multispot antibody differentiation assay.

NOTE: A “licensed” assay refers to a US FDA-approved assay, which is required for all IND studies.
- Hepatic steatosis as demonstrated by liver fat fraction $\geq 5\%$ on $^1\text{H-MRS}$
- Hepatitis C antibody negative, or, if Hepatitis C antibody positive, either: a) known clinical disease, successful therapy ≥ 1 year prior to baseline and undetectable HCV RNA, or b) HCV resolved spontaneously and undetectable HCV RNA. Hepatitis B surface antigen negative at screen visit
- For females ≥ 50 yo, negative mammogram within 1 year of baseline visit
- If use of Vitamin E ≥ 400 IU daily (in any formulation), stable dose for ≥ 6 months prior to study.

10.1.2 Exclusion criteria:

- Heavy alcohol use defined as consumption of more than 20g daily for women or more than 30g daily for men for at least 3 consecutive months over the past 5 years assessed using the Lifetime Drinking History Questionnaire [66, 67];
- Use of insulin or thiazolidinediones (TZDs), or HbA1c $\geq 7\%$. Individuals with mild diabetes that is well-controlled with diet and/or oral anti-diabetic agents besides TZDs will be included. Use of oral anti-diabetics must have been stable for ≥ 6 months prior to study entry.
- Known diabetic retinopathy.
- Known cirrhosis, or Child-Pugh score ≥ 7 , stage 4 fibrosis on biopsy, or clinical evidence of cirrhosis or portal hypertension on imaging or exam. If a subject is not known to be cirrhotic at screen but is found to be cirrhotic based on the results of liver biopsy at baseline, this subject will be referred to a hepatologist for clinical care and will be excluded from further participation in the study.

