11.1.3 Device Studies: N/A

11.1.4 Study Product Supply and Accountability

Tesamorelin and identical placebo will be procured from Theratechnologies, Inc. (Montreal, Canada). Medication will be dispensed by the MGH and NIH Research Pharmacies. A three month supply of medication will be dispensed to patients at the baseline, 3, 6, 9, 12, and 15 month visits. Medication and supplies dispensed will be as follows:

- 190 vials of study drug, comprising a 95 day supply
- 100 vials of sterile water, to be used to reconstitute study drug. A total of 2.2 cc of sterile water is used for the reconstitution of the medication in both vials, and 2cc solution is withdrawn and administered.
- 100 3cc syringes with 18 gauge, 1.5 inch needles.
- 100 additional 18 gauge, 1.5 inch needles
- 95 27 gauge, ½ inch needles
- Box of alcohol swabs
- Sharps container
- Cooler with 2 ice packs for transporting medication home
- Study drug diary

At each dispensation, the subject's identity will be confirmed using 2 identifiers that match the prescription labeling, and the randomization number will also be verified. The number of vials provided will be recorded, along with the Lot # for the medication and, if applicable, kit and/or box #s as well.

The MGH and NIH research pharmacies will receive vials of tesmorelin and placebo from Theratechnologies. The pharmacies will be able to identify which vials are active vs. placebo, but this will not be apparent to investigators or subjects by inspecting the vials.

Subjects will be asked to return used and unused medication at the 3, 6, 9, 12, 15, and 18 month visits. The number of used and unused vials will be recorded prior to destruction of used and unused drug.

Each site will keep track of study drug supply on hand, as well as study drug dispensed to each patient. Overall accountability for this will be shared by the investigator and the research pharmacy, with specific responsibilities delegated by the investigator at each site.

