12.1.3 Screen Visit (to determine eligibility)

- Informed consent
- Detailed H&P and medications (past and current), Lifetime Drinking History assessment
- Blood sampling (AST, ALT, creatinine, total bilirubin, PT (and INR) and PTT, CBC, CD4, HbA1c, HIV viral load, Hepatitis B sAg, Hepatitis C antibody*, PSA (male subjects).
*Positive Hep C antibody patients will be tested for HCV RNA.
- ¹H-MRS/MRI of abdomen for quantification of liver fat and to exclude abnormal liver lesions. (This scan will also be used to assess VAT for those eligible subjects participating in the baseline visit.)

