12.1.4 Randomization and Subsequent Visits

Eligible subjects will return for 9 visits. After signing consent and, prior to the baseline visit, subjects will be randomized in a 1:1 ratio to receive GHRH¹⁻⁴⁴ 2mg SC QD versus identical-appearing placebo as above. Randomization will be stratified by study site and vitamin E use ≥ 400 IU daily of any formulation. Permuted block randomization will be performed by an MGH biostatistician, with randomization lists distributed to the MGH and NIH pharmacies. Study staff, investigators, and subjects will be blinded to assignment. During the first 12-month treatment phase, subjects will have visits at baseline, 2 weeks, and months 3, 6, 9 and 12. After month 12, all patients will receive open label GHRH regardless of their original randomization. Subsequent visits will take place at months 12.5, 15 and 18 months. Subjects seen at MGH will receive stable isotope study and euglycemic hyperinsulinemic clamp in addition to other study procedures.

12.1.5 Baseline assessment: The baseline assessment will be completed within 3 months of the screening visit. In order to complete all of the procedures in the baseline assessment, subjects may come for up to 3 different visits, all of which should take place within a 2 week period. Subjects will begin the study drug upon completion of the baseline assessment, and subsequent visits will be timed according to the day study drug is started.

- H&P
- Fasting labs: IGF-I, AST, ALT, GGT, alkaline phosphatase, lipid panel including direct LDL, frozen serum for adiponectin, IL-6, CRP, CK18, and other relevant inflammatory biomarkers, as guided by the histological results
- Height, metabolic weight, anthropometrics
- Whole body DEXA scan for regional fat
- 4-day food record and Modifiable Activity Questionnaire
- OGTT

- Transient elastography (“FibroScan”)
- Liver biopsy. Biopsy will not be done if performed in the 6 months prior to baseline and, in the interval since biopsy, no new treatment initiated and no weight change $\geq 8\%$ of baseline weight
- Peripheral blood mononuclear cells (PBMCs) will be processed and stored
- Subjects at MGH will receive stable isotopes and clamp for metabolic assessment (see below).

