12.2.3 Total Blood Volume

The total blood drawn for subjects completing the study is equivalent to approximately 730 cc over a period of 18 months for those subjects in the subset receiving euglycemic hyperinsulinemic clamp and stable isotopes at MGH, and approximately 540cc over 18 months for those at NIH (where clamp/isotope will not be performed). The maximum amount of blood drawn at any given visit will be approximately 170cc, which will be drawn at the baseline and 12 month visits. A total of 730cc (less than 2 blood donations) over 18 months does not pose excessive risk to patients, nor does withdrawal of up to 170cc at a single timepoint.

Patients with a hemoglobin < 11 g/dL will be excluded from the study.

The amount of blood drawn for research purposes will be within the limits allowed for adult subjects at the NIH Clinical Center (Medical Administrative Series Policy M95-9 Guidelines for Limits of Blood Drawn for Research Purposes in the Clinical Center: <http://cc-internal.cc.nih.gov/policies/PDF/M95-9.pdf>). The amount is also within Partners Human Research Committee guidelines (MGH IRB).

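### No glucose is scheduled before randomization and no exclusion matches the fasting-glucose stopping limit, so a subject already above that limit can be randomized and biopsied (minor; frequency unknown)

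*Combined protocol and SAP*

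**What the plan says.** **Entry.** Section 10.1.2 excludes "Use of insulin or thiazolidinediones (TZDs), or HbA1c" of 7% or more. Mild diabetes controlled by diet or by stable oral agents other than TZDs is allowed. No exclusion names a fasting glucose.

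**Screening.** Section 12.1.3 lists "Blood sampling (AST, ALT, creatinine, total bilirubin, PT (and INR) and PTT, CBC, CD4, HbA1c, HIV viral load, Hepatitis B sAg", then hepatitis C antibody and PSA. Glucose is not listed there, and the screen column of Appendix A has none.

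**Randomization.** Section 15.5 places it one to two weeks before the baseline visit, so that the pharmacy can prepare the drug.

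**Baseline.** Section 12.1.5 says: "The baseline assessment will be completed within 3 months of the screening visit". For the procedures, "subjects may come for up to 3 different visits, all of which should take place within a 2 week period". They include an OGTT, whose first glucose sample is at 0 minutes (12.3.5), and a liver biopsy unless a recent one qualifies. The order is not fixed. "Subjects will begin the study drug upon completion of the baseline assessment", and 18.4.4 has administration observed on site at the baseline visit.

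**Stopping.** Section 14.3.1 permanently discontinues the intervention for fasting glucose above 150 mg/dL, or above 180 mg/dL "for individuals with known type 2 diabetes at study entry, at any visit, confirmed by re-draw". Section 14.4.5 gives the same limits and the steps: contact the subject, re-draw, and discontinue if the value persists. It also says that fasting glucose is checked at each visit.

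**The concern.** The plan uses one glycaemic measure to admit subjects and another to remove them, and does not measure the second until after randomization. A subject can satisfy every entry criterion while already meeting a criterion for permanent discontinuation.

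Such a subject takes one of the 60 randomized places. They may also have a percutaneous biopsy of up to three passes (12.3.3), with the risks listed in 18.4.3 (pain, transient hypotension, bleeding, transient bacteremia). At MGH they may also have the isotope and clamp study, in which insulin runs until 360 minutes (12.3.11). They are then stopped for a value that the drug did not cause. Randomization numbers are not re-used (15.5), and no replacement is described. What is at stake is avoidable procedures and a poorly used place.

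**Working it through.** The documents give no rate of affected subjects and no relation between HbA1c and fasting glucose. The check is therefore a walk through the schedule, not a calculation.

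1. **Can an eligible subject be above the limit?** The stopping limit is >150 mg/dL, or >180 mg/dL with known type 2 diabetes (14.3.1, 14.4.5). The entry limits are HbA1c <7%, no insulin and no TZD (10.1.2). Nothing in 10.1.1 or 10.1.2 refers to fasting glucose, so HbA1c <7% with a fasting glucose above the limit meets every glycaemic criterion.
2. **Scheduled glucose values before randomization.** Screening bloods (12.1.3): none. Appendix A screen column: none. Randomization precedes baseline (12.1.4, 15.5). Count: 0.
3. **Scheduled fasting glucose before the first dose.** The baseline OGTT 0-minute sample (12.1.5, 12.3.5) is one value for every subject. MGH subjects also have bedside readings from time 0 of the isotope and clamp study (12.3.11). NIH subjects have no clamp.
4. **Does the stopping rule reach that baseline value?** Yes. It applies at any visit, and drug starts only when the baseline assessment is complete.
5. **Must the value be seen before the biopsy?** No. Baseline may spread over three visits in two weeks in any order, and 12.1.5 and 12.3.3 do not make the biopsy depend on a glucose result.
6. **Must the value, and its re-draw, be seen before the first dose?** No. Section 14.4.5 calls for a re-draw but does not hold dosing meanwhile. If the re-draw follows the first dose, the confirming value is no longer pre-drug, although the 0-minute value still is.
7. **Is there a comparable rule elsewhere?** Yes. Section 10.1.2 says what happens when the baseline biopsy reveals cirrhosis: referral and exclusion from further participation. For a high baseline glucose there is only the general stopping rule.

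One affected subject is 1/60 = 1.7% of the randomized places.

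**The case against.** The strongest case against is that most of this is already covered.

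- **Entry is gated on glycaemia.** HbA1c of 7% or more, insulin and TZDs are excluded, and oral agents must have been stable for at least six months. Using HbA1c for entry and fasting glucose for on-study safety is a reasonable choice, and the affected group is probably small. This stands, and it is why the point is minor.
- **A pre-dose fasting value exists for everyone.** A reader might infer from Appendix A, where the fasting glucose row starts at 0.5 months, that no fasting glucose precedes dosing. That is not so: the row is blank at baseline, 12 and 18 months because an OGTT is done at those visits. Dosing an affected subject requires a site to proceed before acting on a value, or before the re-draw is back. At MGH the investigator also uses the fasting glucose to set the dextrose rate. This largely answers the concern about the first dose. It does not answer randomization or the biopsy.
- **Section 14.4.5 says glucose is checked at every visit.** It sets no entry limit, and neither 12.1.3 nor Appendix A carries it into screening.
- **The plan accepts late removals.** Baseline cirrhosis is one example, and 15.4 allows for 20% to 25% discontinuation. True, but cirrhosis may become known only from the biopsy, whereas a high fasting glucose can be found with one blood test beforehand.
- **One sentence in 12.1.5 would cover biopsy and dosing.** Correct. The screening assay adds only protection of the randomized place, and it is cheap.

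**Conclusion.** The mismatch is real and of the lowest severity. Followed exactly, the plan can randomize and biopsy a subject who already meets its own stopping rule, and it does not require the baseline fasting value to be reviewed before the biopsy or the first dose.

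Its size cannot be computed. The conclusion assumes only that HbA1c below 7% does not rule out a fasting glucose above the limit; the documents neither state nor exclude this. Not every subject would have the biopsy, since a recent qualifying biopsy or a contraindication removes it (12.1.5, 12.3.3).

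Two stronger readings are not supported:

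- **Loss of power.** A reader might infer that such stops erode the stated 82%. The documents give no number of affected subjects, and these stops may fall within the discontinuation already allowed for in 15.4. The stated power does not change.
- **Damage to the safety or efficacy comparison.** The baseline OGTT preserves a pre-drug fasting value, and the intention-to-treat analysis in 15.8.4 retains the subject's available data.

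**What to change.** 1. In 12.1.5, require the OGTT fasting sample to be taken first. Require it to be reviewed, with a re-draw if it is above the limit, before the baseline biopsy and before the first dose.
2. In 12.1.3 and Appendix A, add a fasting glucose to the screening bloods on the day of the MRS, which already needs a 12-hour fast (12.3.1). In 10.1.2, exclude a confirmed value >150 mg/dL, or >180 mg/dL with known type 2 diabetes, to match 14.3.1 and 14.4.5.

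Both are useful. Baseline can fall up to three months after screening, so a screening value alone may be out of date; the baseline check alone comes after the place has been used.

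The cost is one assay, a fasting instruction for the screening blood, a possible re-draw, an ordering constraint within the existing three-visit, two-week window, and a few screen failures. Those would be almost only subjects whom the stopping rule would remove anyway. The endpoint, analysis and sample size are untouched.
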